3.1.4. Safety Analysis Set

The Safety Analysis Set is the primary analysis set for safety analyses. Safety analysis sets are defined for this study:

- The Safety Analysis Set includes all participants who were randomized and received at least 1 dose of study drug. This is the primary analysis set for safety analyses for whole study period. This analysis set will also be used to describe baseline information.
- The Safety Analysis Set for LA Regimen includes all randomized participants who have received at least one dose of the complete long acting study drug regimen (ie, SC LEN + GS-5423 and GS-2872). This is the primary analysis set for safety analyses for LA regimen period analysis.

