5.3. Dosage and Administration of GS-5423, GS-2872, and Lenacapavir

On Day 1, all participants will receive the following study regimen:

- Oral LEN 600 mg will be administered orally (PO) with approximately 240 mL water, without regard to food.
- LEN 927 mg SC will be administered within 30 minutes after oral LEN for loading, as 2 SC injections at separate injection sites in the abdomen, within 15 minutes.
- GS-5423 30 mg/kg IV infusion will be administered immediately following (up to 1 hour after) the last SC LEN injection.
- GS-2872 10 mg/kg or 30 mg/kg (depending upon treatment group assignment) IV infusion will be administered at least 15 minutes following, and up to 1 hour after, the completion of GS-5423 IV infusion per [Table 5-1](#).

On Day 1, all study drugs should be administered on the same day (ie, no visit window is permitted for Day 1 study drug administration).

On Day 2, all participants will self-administer oral LEN for loading 600 mg with approximately 240 mL water, without regard to food, at approximately the same time as the oral LEN dose for loading on Day 1.

Dose and administration of LEN, GS-5423, and GS-2872 for Treatment Groups 1 and 2 are described below.

Table 5-1. Treatment Table

Study Day	Treatment Group 1	Treatment Group 2
Day 1	LEN 600 mg (two 300 mg tablets, PO) LEN 927 mg (two 1.5 mL injections, SC) GS-5423 30 mg/kg (IV infusion) GS-2872 10 mg/kg (IV infusion)	LEN 600 mg (two 300 mg tablets, PO) LEN 927 mg (two 1.5 mL injections, SC) GS-5423 30 mg/kg (IV infusion) GS-2872 30 mg/kg (IV infusion)
Day 2	LEN 600 mg (two 300 mg tablets, PO)	LEN 600 mg (two 300 mg tablets, PO)

IV = intravenous; LEN = lenacapavir; PO = per oral; SC = subcutaneous

Supportive medications, including but not limited to diphenhydramine, acetaminophen, and steroids, will be available in the clinic settings during the IV infusions.

Study drug infusion will be temporarily stopped if an infusion-related adverse reaction occurs. Symptom severity will be evaluated, and supportive medications provided as clinically indicated. Study drug infusion may be slowed and resumed after symptoms have resolved if approved by the investigator. If the symptoms, in the judgment of the investigator, compromise the ability to continue study-specific procedures and are considered to not be in the participant's best interests, or recurrent symptoms prevent completion of infusion, the infusion will be permanently discontinued.

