8.3.1.3. Safety

The primary analysis set for safety analyses is defined as the Safety Analysis Set, which will include all randomized participants who have received at least one dose of study drug.

All data collected during study will be included in the safety summaries.

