7.1.7. Additional Analysis of Adverse Events

7.1.7.1. Study Drug Related Injection Site Reactions and Infusion Related Reactions

Additional analysis of AEs will be performed for injection site reaction (ISR) as defined by high level term (HLT) of "Injection site reactions", and infusion related reaction (IRR) as defined per eCRF (ie, AE with "Yes" answer to "Is this part of an infusion-related reaction?" in AE CRF), respectively. The following summaries will be provided for LA regimen period analysis only.

- Number of participants received any injection or infusion
- Number and percentage of participants with study drug related ISRs or IRRs
- Number and percentage of participants with study drug related ISRs or IRRs by grade
- Number and percentage of participants with study drug related ISRs or IRRs by PT

The denominator for the percentage calculation will be based on the number of participants received at least one injection or infusion in Safety Analysis Set .

Duration of the ISR will also be calculated and summarized. Duration of a given ISR event is defined as the ISR stop date minus the ISR onset date plus 1 day. For ISRs with ongoing stop date, stop date will be imputed as last study date or database finalization date, whichever is the earliest. Duration of ISR events in days will be summarized by PT and overall using descriptive statistics. Duration of a given IRR event is defined as the IRR stop date minus the IRR onset date plus 1 day, and duration of IRR will be listed also.

By-participant listings for ISRs or IRRs will be provided.

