7.7. Changes from Protocol-Specified Safety Analyses

No change from protocol-specified safety analyses is planned.

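### LA-period safety is analysed in a complete-regimen set, so an adverse event that keeps a later long-acting drug from being started removes the participant from the only tables that approximate the Week 26 primary endpoint

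*SAP*

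**What the plan says.** Protocol 8.3.1.3 defines a single safety set, "all randomized participants who have received at least one dose of study drug", and Protocol 8.6 uses it for all safety summaries. The primary endpoint is the incidence of treatment-emergent SAEs through Week 26 (Protocol 8.1.2, repeated in SAP 7).

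SAP 3.1.4 keeps that set for the whole study period and adds another: "The Safety Analysis Set for LA Regimen includes all randomized participants who have received at least one dose of the complete long acting study drug" combination, with all three of SC LEN, GS-5423 and GS-2872 required. It then states: "This is the primary analysis set for safety analyses for LA regimen period analysis". SAP section 3 limits the data entering the LA Regimen Period Analysis to the same participants, and SAP 7.1.6 carries this into the adverse-event tables. SAP 7.7 reports: "No change from protocol-specified safety analyses is planned".

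Under Protocol 5.3 the Day 1 drugs are given in sequence: oral LEN, SC LEN, GS-5423, and GS-2872 last. If an infusion reaction is judged to compromise the participant, or if "recurrent symptoms prevent completion of infusion, the infusion will be permanently discontinued".

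On injection-site and infusion-related reactions (ISRs and IRRs), SAP 7.1.7.1 says: "The following summaries will be provided for LA regimen period analysis only". The percentages are "based on the number of participants received at least one injection or infusion in Safety Analysis Set".

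**The concern.** Safety and tolerability are the primary objective. A safety population should not depend on how well the participant tolerated dosing. Here, entry to the LA-period set requires receipt of a drug given after the SC injection and after another infusion. If an adverse event on Day 1 means that GS-2872 is never started, that event decides whether the participant is counted. The bias in the LA-period tables runs in one direction, toward fewer events. The LA-period table of adverse events leading to premature discontinuation of study drug also loses anyone whose dosing was cut short before the last drug.

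The reaction summaries raise a second question. They are confined to the LA period, but their denominator refers to the general Safety Analysis Set. A participant could then count below the line while the reaction is left out above it.

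**Working it through.** **Step 1: which window matches the primary endpoint.** SAP 7.1.5.1 gives two windows for treatment-emergent events. One ends at the last exposure date of the LA regimen, in practice ART restart at about Week 26. The other ends at the last exposure date, about Week 52. Only the first approximates an endpoint counted through Week 26, and it is the one tied to the complete-regimen set.

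**Step 2: who is in which set.** Reading Protocol 8.3.1.3, SAP 3.1.4 and SAP 7.1.7.1 together:

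| Dosing received | Any-dose safety set | LA-regimen safety set | Denominator in 7.1.7.1 |
|---|---|---|---|
| Oral LEN only | in | out | out |
| SC LEN given, GS-5423 never started | in | out | in |
| SC LEN and GS-5423 given, GS-2872 never started | in | out | in |
| All three started, an infusion not completed | in | unclear | in |
| All three in full | in | in | in |

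The fourth row is unclear because *complete* is not defined. The Full Analysis Set uses the same complete-regimen wording (SAP 3.1.2), and SAP 3.1.3 then removes partial or missed doses from it to form the Per Protocol set. This suggests that partly dosed participants can be in the complete-regimen sets. Exclusion is certain only when a long-acting drug was never started.

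**Step 3: reproduce the plan's own limits.** Protocol Table 8-1 and SAP Table 1-1 give Clopper-Pearson limits for n = 20.
- 0 events: upper limit = 1 − 0.025^(1/20) = 16.8%. The table has 16.8%.
- 1 event: lower limit = 1 − 0.975^(1/20) = 0.1%. The upper limit p solves (1 − p)^20 + 20p(1 − p)^19 = 0.025, so p = 24.9%. The table has 0.1% and 24.9%.

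**Step 4: the same method with and without the excluded participant.** Let k be the number of participants for whom a long-acting drug was never started because of an adverse event, each with one event of the type tabulated. The documents give no value, so k is an assumption. For k = 1 and no other events, the LA set gives 0/19 with upper limit 1 − 0.025^(1/19) = 17.6%.

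| Setting | Any-dose set | LA-regimen set |
|---|---|---|
| n = 20, k = 1, no other events | 1/20 = 5.0% (0.1 to 24.9) | 0/19 = 0% (0 to 17.6) |
| n = 20, k = 1, one other event | 2/20 = 10.0% (1.2 to 31.7) | 1/19 = 5.3% (0.1 to 26.0) |
| n = 20, k = 2, no other events | 2/20 = 10.0% (1.2 to 31.7) | 0/18 = 0% (0 to 18.5) |
| One group of 10, k = 1, no other events | 1/10 = 10.0% (0.3 to 44.5) | 0/9 = 0% (0 to 33.6) |
| Pooled cohorts at 40, k = 1, no other events | 1/40 = 2.5% (0.1 to 13.2) | 0/39 = 0% (0 to 9.0) |

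**Step 5: the reaction tables.** If the numerator is limited to LA-period participants and the denominator is everyone injected or infused in the any-dose set, the case n = 20, k = 1 with no other reactions gives 0/20 (upper limit 16.8%) where one consistent population gives 1/20. This needs SAP section 3, 3.1.4 and 7.1.7.1 to be combined in that way; 7.1.7.1 does not itself name the numerator set.

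**The case against.** Four points on the other side deserve weight.

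*The events are not lost.* The any-dose set stays primary for the whole-study analysis, which tabulates SAEs, all treatment-emergent events and events leading to discontinuation (SAP 7.1.6). All adverse events, SAEs and reactions are also listed. A reader might infer that a serious Day 1 reaction could vanish from the report. It could not: it would be counted in the whole-study SAE table. What is missing is its place in a Week 26 rate.

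*The stop rule is narrower than it looks.* A reader might infer that everyone whose dosing was stopped for an infusion reaction is removed. Protocol 5.3 discontinues the infusion concerned. It does not say that the next drug is withheld, and it does not address reactions to LEN. A participant stopped part-way through GS-2872 may well remain in the LA set.

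*The mismatch in 7.1.7.1 is an inference.* Everyone in the LA-regimen set has had an injection and both infusions, so restricting that set to participants injected or infused would be pointless. The wording may therefore intend the any-dose set throughout, or may be loose shorthand for the LA set. Either reading removes the mismatch. This stands: it is an ambiguity, not a demonstrated error.

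*No effect on the Week 26 primary analysis is shown.* This SAP covers the final analysis. SAP 2.2 says the primary analysis has already been done, and the documents do not show which set it used.

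A complete-regimen population is also a reasonable supplementary view, and the protocol already uses one for efficacy. None of this explains why it should be primary for LA-period safety, or why SAP 7.7 records no change when SAP 6.3 does record the change to the Full Analysis Set.

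**Conclusion.** The point stands in this form. The SAP replaces the protocol's any-dose set with a complete-regimen set in the one safety window that approximates the primary endpoint, and does not declare it. The exclusion depends on outcome for any participant whose adverse event means that a later long-acting drug is never started. At these sample sizes, one such participant can decide whether an LA-period row reads zero: 5.0% against 0% in 20, or 10.0% against 0% in a group of 10.

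The size is hypothetical. It assumes that such a stop occurred and that the participant had the event being tabulated, serious in the case of the SAE table. If every participant received all three drugs, the two safety sets coincide and nothing changes. The documents do not support saying that reported rates are in fact biased, that all participants with a stopped infusion are dropped, or that the reaction percentages certainly mix two populations.

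**What to change.** 1. In SAP 3.1.4 and section 3, make the protocol Safety Analysis Set (at least one dose of any study drug) primary for safety up to ART restart or Week 26, as well as for the whole study. State that this set supplies the Week 26 SAE endpoint.
2. Keep the complete-regimen set as supportive, and define *complete*, including how a partly given infusion is classified.
3. In SAP 7.1.7.1, name one population for numerator and denominator, drawn from the any-dose set: at least one SC injection for ISRs, at least one started infusion for IRRs.
4. Record any remaining departure from the protocol in SAP 7.7.

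The cost is SAP wording and a population flag, with no new data. LA-period rates may become slightly less favourable.

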3.1.5. Pharmacokinetic (PK) Substudy Analysis Set

The LEN PK Substudy Analysis Set includes all randomized participants who are enrolled in the optional PK Substudy, have received at least 1 dose of study drug, and have at least 1 nonmissing LEN concentration value reported by the PK laboratory test.

3.1.6. Pharmacokinetic (PK) Analysis Sets

The PK Analysis Sets include the follows:

- LEN PK Analysis Set includes all randomized participants who have received at least 1 dose of study drug, and have at least 1 nonmissing LEN concentration value reported by the PK laboratory test.
- GS-5423 PK Analysis Set includes all randomized participants who have received at least 1 dose of study drug, and have at least 1 nonmissing GS-5423 concentration value reported by the PK laboratory test.
- GS-2872 PK Analysis Set includes all randomized participants who have received at least 1 dose of study drug, and have at least 1 nonmissing GS-2872 concentration value reported by the PK laboratory test.

3.1.7. Immunogenicity Analysis Sets

The Immunogenicity analysis sets include the follows:

- Anti-GS-5423 Immunogenicity Analysis Set will include all randomized participants who have received at least 1 dose of study drug and have had at least 1 nonmissing value for anti-GS-5423 evaluation.
- Anti-GS-2872 Immunogenicity Analysis Set will include all randomized participants who have received at least 1 dose of study drug and have had at least 1 nonmissing value for anti-GS-5423 evaluation.
- Anti-GS-5423 and Anti-GS-2872 Immunogenicity Analysis Set will include all randomized participants who have received at least 1 dose of study drug and have had at least 1 nonmissing value for both anti-GS-5423 and anti-GS-2872 evaluation.

3.2. Participant Grouping

For analyses based on the All Randomized Analysis Set or the FAS, participants will be grouped according to the treatment group to which they were randomized. For all other analyses, participants will be grouped according to the actual treatment received. The actual treatment received will differ from the randomized treatment only when their actual treatment differs from randomized treatment for the entire treatment duration. Templates of participant grouping can be found in [Appendix 6](#).

3.2.1. Grouping for Enrollment, Eligibility, Disposition, Demographics, Baseline Characteristics and Safety Analyses

For enrollment, eligibility, protocol deviation, disposition, demographics, baseline characteristics including baseline ARVs and safety analyses, participants will be grouped as follows for table summary:

- **Primary Cohort**
 - Treatment Group 1: SC LEN + GS-5423 + GS-2872 10 mg/kg
 - Treatment Group 2: SC LEN + GS-5423 + GS-2872 30 mg/kg
 - Total Primary Cohorts: All participants from Treatment Groups 1 and 2 (for all tables and figure summary unless specified otherwise)
- **Pilot Cohort**
 - Treatment Group 1: SC LEN + GS-5423 + GS-2872 10 mg/kg
 - Treatment Group 2: SC LEN + GS-5423 + GS-2872 30 mg/kg
 - Total Pilot Cohorts: All participants from Treatment Groups 1 and 2 (for all tables and figure summary unless specified otherwise)
- **Pooled Cohorts**
 - Total Pooled Cohorts: All participants from pooled Treatment Groups 1 and 2 (for all tables and figure summary unless specified otherwise)

3.2.2. Grouping for Efficacy Analyses

For efficacy analyses, participants will be grouped as follows for table summary:

- **Primary Cohort**
 - Treatment Group 1: SC LEN + GS-5423 + GS-2872 10 mg/kg
 - Treatment Group 2: SC LEN + GS-5423 + GS-2872 30 mg/kg
 - Total Primary Cohorts: All participants from Treatment Groups 1 and 2 (for all tables and figure summary unless specified otherwise)
- **Pilot Cohort**
 - Treatment Group 1: SC LEN + GS-5423 + GS-2872 10 mg/kg
 - Treatment Group 2: SC LEN + GS-5423 + GS-2872 30 mg/kg
 - Total Pilot Cohorts: All participants from Treatment Groups 1 and 2 (for all tables and figure summary unless specified otherwise)

No pooled analyses will be conducted on the efficacy.

3.2.3. Grouping for PK and Immunogenicity Analyses

For PK analysis of GS-5423 and LEN, as well as immunogenicity analysis of GS-5423 and GS-2872, participants will be grouped as follows for table summary:

- Primary Cohort
 - Treatment Group 1: SC LEN + GS-5423 + GS-2872 10 mg/kg
 - Treatment Group 2: SC LEN + GS-5423 + GS-2872 30 mg/kg
 - Total Primary Cohorts: All participants from Treatment Groups 1 and 2 (for all tables and figure summary unless specified otherwise)
- Pilot Cohort
 - Treatment Group 1: SC LEN + GS-5423 + GS-2872 10 mg/kg
 - Treatment Group 2: SC LEN + GS-5423 + GS-2872 30 mg/kg
 - Total Pilot Cohorts: All participants from Treatment Groups 1 and 2 (for all tables and figure summary unless specified otherwise)
- Pooled Cohorts
 - Treatment Group 1: SC LEN + GS-5423 + GS-2872 10 mg/kg
 - Treatment Group 2: SC LEN + GS-5423 + GS-2872 30 mg/kg
 - Total Pooled Cohorts: All participants from pooled Treatment Groups 1 and 2 (for all tables and figure summary unless specified otherwise)

For PK analysis of GS-2872, participants will be grouped as follows for table summary:

- Primary Cohort
 - Treatment Group 1: SC LEN + GS-5423 + GS-2872 10 mg/kg
 - Treatment Group 2: SC LEN + GS-5423 + GS-2872 30 mg/kg
- Pilot Cohort
 - Treatment Group 1: SC LEN + GS-5423 + GS-2872 10 mg/kg
 - Treatment Group 2: SC LEN + GS-5423 + GS-2872 30 mg/kg
- Pooled Cohorts
 - Treatment Group 1: SC LEN + GS-5423 + GS-2872 10 mg/kg

— Treatment Group 2: SC LEN + GS-5423 + GS-2872 30 mg/kg

PK results of GS-2872 will not be summarized across the treatment groups.

3.3. Strata and Covariates

There is no stratification for randomization for the Primary Cohort.

Regarding the optional Pilot Cohort, randomization has been stratified by the antibody (GS-5423 or GS-2872) to which the participant is sensitive, but the strata will not be used in the analyses because of the small sample size of the study.

3.4. Examination of Participant Subgroups

There are no prespecified participant subgroupings for efficacy and safety analyses due to the small sample size.

3.5. Multiple Comparisons

Adjustments for multiplicity will not be conducted in this phase 1b trial.

3.6. Missing Data and Outliers

3.6.1. Missing Data

In general, missing data will not be imputed unless methods for handling missing data are specified. Exceptions are presented in this document.

The handling of missing or incomplete dates for AE onset is described in Section 7.1.5.2 and for prior and concomitant medications in Section 7.4.

Missing PK sampling dates may be imputed based on other visit information. Missing PK sampling times may be imputed to nominal times. Missing drug concentrations will not be imputed.

3.6.2. Outliers

Outliers will be identified during the data management and data analysis process, but no sensitivity analyses will be conducted. All data will be included in the data analysis.

Individual study drug concentration values may be identified as outliers by the clinical pharmacokineticist and excluded from concentration summary tables and figures and from the noncompartmental PK analysis. Outlier drug concentrations will be identified in the concentration listing along with the justification for exclusion.

3.7. Data Handling Conventions and Transformations

3.7.1. Data Handling Conventions and Transformations for Non-PK Data

Only year of birth is collected in this study. The following conventions will be used for the imputation of date of birth when it is partially missing or not collected:

- If year of birth is collected, “01 July” will be imputed as the day and month of birth
- If year of birth is missing, date of birth will not be imputed.

In general, age collected at Day 1 (in years) will be used for analyses and presented in listings. If age at Day 1 is not available for a participant, age derived based on date of birth and the Day 1 visit date will be used instead. If a randomized participant was not dosed with any study drug, the randomization date will be used instead of the Day 1 visit date. For screen failures, the date the first informed consent was signed will be used for the age derivation. Age required for longitudinal and temporal calculations and analyses (eg, estimates of creatinine clearance) will be based on age derived from date of birth and the date of the measurement or event, unless otherwise specified.

HIV-1 RNA results of ‘No HIV-1 RNA detected’ and “<20 cp/mL HIV-1 RNA Detected” will be imputed as 19 copies/mL for analysis purposes.

For other non-PK data that are continuous in nature but are less than the lower limit of quantification (LLOQ) or above the upper limit of quantification (ULOQ) will be imputed as follows:

- A value that is 1 unit less than the LLOQ will be used to calculate descriptive statistics if the datum is reported in the form of “< x” (where x is considered the LLOQ). For example, if the values are reported as < 50 and < 5.0, values of 49 and 4.9, respectively, will be used to calculate summary statistics. An exception to this rule is any value reported as < 1 or < 0.1, etc. For values reported as < 1 or < 0.1, a value of 0.9 or 0.09, respectively, will be used to calculate summary statistics.
- A value that is 1 unit above the ULOQ will be used to calculate descriptive statistics if the datum is reported in the form of “> x” (where x is considered the ULOQ). Values with decimal points will follow the same logic as above.
- The limit of quantification will be used to calculate descriptive statistics if the datum is reported in the form of “≤ x” or “≥ x” (where x is considered the limit of quantification).

3.7.2. Data Handling Conventions and Transformations for PK Data

Natural logarithmic transformation will be used for non-BLQ drug concentrations and analysis of PK parameters. Concentration values that are below the limit of quantitation (BLQ) will be presented as “BLQ” in the concentration data listing.

For summary statistics, BLQ values will be treated as zero at predose and postdose time points. At predose, if all concentration values are BLQ, then the mean, and order statistics (minimum, Q1, median, Q3, and maximum) will be displayed as 0 and the rest of the summary statistics (ie, SD and CV) will be missing. If any predose concentration values are non-BLQ, then the number of samples, order statistics, and all summary statistics will be displayed.

At any given postdose time point, if more than one-third of the participants have a concentration value of BLQ, then only the number of samples and order statistics will be displayed in the summary table; otherwise, order statistics and summary statistics will be displayed in the summary table.

The following conventions will be used for the presentation of order statistics for postdose time points in the summary table:

- If at least 1 participant has a concentration value of “BLQ” for the time point, the minimum value will be displayed as “BLQ”.
- If more than 25% of the participants have a concentration value of “BLQ” for a given time point, the minimum and Q1 values will be displayed as “BLQ”.
- If more than 50% of the participants have a concentration value of “BLQ” for a given time point, the minimum, Q1, and median values will be displayed as “BLQ”.
- If more than 75% of the participants have a concentration value of “BLQ” for a given time point, the minimum, Q1, median, and Q3 values will be displayed as “BLQ”.
- If all participants have concentration values of “BLQ” for a given time point, all order statistics (minimum, Q1, median, Q3, and maximum) and summary statistics will be displayed as “BLQ”.

Similarly, for PK concentration plottings, if more than one-third of the participants have a concentration values of BLQ, then the mean and standard deviation are not displayed at that timepoint; and if more than one-half of the participants have a concentration values of BLQ, then the median and quartiles are not displayed at that timepoint.

Concentration related PK parameters (eg, C_{max} and C_{26wk}) that are BLQ will be excluded before log transformation or statistical model fitting and displayed as described above.

